13.2 TOXICITY CRITERIA

The following adverse event management guidelines are intended to ensure the safety of each patient while on the study. The descriptions and grading scales found in the revised NCI Common Terminology Criteria for Adverse Events (CTCAE) version 4.0 will be utilized for AE reporting until March 31, 2018. CTCAE version 5.0 will be utilized for AE reporting beginning April 1, 2018. All appropriate treatment areas should have access to a copy of the CTCAE version 5.0. A copy of the CTCAE version 5.0 can be downloaded from the CTEP web site (http://ctep.cancer.gov/protocolDevelopment/electronic_applications/ctc.htm#ctc_40).

13.2.1 Toxicity Grading for Vaccinia Toxicity ³³

Grade 1: Cutaneous reaction extending no more than 10 cm from the vaccination site (i.e., limited to the upper arm)

Grade 2: Any autoinoculation syndrome that resolves without sequelae; Generalized vaccinia extending more than 10 cm from the vaccination site

Grade 3: Any toxicity that is between grade 2 and 4

Grade 4: Autoinoculation syndrome (e.g. blindness); post vaccinia encephalitis; vaccinia gangrenosum; eczema gangrenosum; Stevens-Johnson syndrome

13.3 DATA REPORTING

Adverse event lists, guidelines, and instructions for AE reporting can be found in Section [7](#).

13.3.1 Method

This study will be monitored by the Clinical Data Update System (CDUS) Version 3.0. Cumulative protocol- and patient-specific CDUS data will be submitted electronically to CTEP on a quarterly basis, either by FTP burst of data or via the CDS web application. Reports are due January 31, April 30, July 31, and October 31. Instructions for submitting data using the CDUS can be found on the CTEP Web site

(<http://ctep.cancer.gov/reporting/cdus.html>).

Note: If your study has been assigned to CDUS-Complete reporting, all adverse events (both routine and expedited) that have occurred on the study and meet the mandatory CDUS reporting guidelines must be reported via the monitoring method identified above. If your study has been assigned to CDUS-Abbreviated reporting, no adverse event reporting (routine or expedited) is required to be reported via CDUS

13.3.2 Responsibility for Data Submission

Participating study sites are responsible for submitting CDUS data and/or data forms to either the Coordinating Center or to the Lead Organization on the study quarterly. The date for submission to the Coordinating Center or to the Lead Organization will be set by them. CDUS does not accept data submissions from the participants on the study. When setting the dates, allow time for Coordinating Center compilation, Principal Investigator review, and timely submission to CTEP by the quarterly deadlines (see Section **13.3**).

Either the Coordinating Center or the Lead Organization is responsible for compiling and submitting CDUS data to CTEP for all participants and for providing the data to the Principal Investigator for review.

13.4 CTEP MULTICENTER GUIDELINES

This protocol will adhere to the policies and requirements of the CTEP Multicenter Guidelines. The specific responsibilities of the Principal Investigator and the Coordinating Center (Study Coordinator) and the procedures for auditing are presented in Appendix B (Section **0**).

- The Principal Investigator/Coordinating Center is responsible for distributing all IND Action Letters or Safety Reports received from CTEP to all participating institutions for submission to their individual IRBs for action as required.
- Except in very unusual circumstances, each participating institution will order DCTD-supplied agents directly from CTEP. Agents may be ordered by a participating site only after the initial IRB approval for the site has been forwarded by the Coordinating Center to the CTEP PIO ([contact]) except for Group studies.

13.5 COLLABORATIVE AGREEMENTS LANGUAGE

The PANVAC™-V (vaccinia) and PANVAC™-F (fowlpox) (hereinafter referred to as Agents) supplied by CTEP, DCTD, NCI used in this protocol is/are provided to the NCI under a Collaborative Agreement (CRADA, CTA, CSA) between BNIT (Bavarian Nordic ImmunoTherapeutics) (hereinafter referred to as “Collaborator(s)”) and the NCI. Therefore, the following obligations/guidelines, in addition to the provisions in the “Intellectual Property Option to Collaborator”

(http://ctep.cancer.gov/industryCollaborations2/intellectual_property.htm) contained within the terms of award, apply to the use of the Agent(s) in this study:

1. Agent(s) may not be used for any purpose outside the scope of this protocol, nor can Agent(s) be transferred or licensed to any party not participating in the clinical study. Collaborator(s) data for Agent(s) are confidential and proprietary to Collaborator(s) and shall be maintained as such by the investigators. The protocol documents for studies utilizing Agents contain confidential information and should not be shared or distributed without the permission of the NCI. If a copy of this protocol is requested by a patient or patient's family member participating on the study, the individual should sign a confidentiality agreement. A suitable model agreement can be downloaded from: <http://ctep.cancer.gov>.
2. For a clinical protocol where there is an investigational Agent used in combination with (an)other Agent(s), each the subject of different Collaborative Agreements, the access to and use of data by each Collaborator shall be as follows (data pertaining to such combination use shall hereinafter be referred to as "Multi-Party Data"):
 - a) NCI will provide all Collaborators with prior written notice regarding the existence and nature of any agreements governing their collaboration with NCI, the design of the proposed combination protocol, and the existence of any obligations that would tend to restrict NCI's participation in the proposed combination protocol.
 - b) Each Collaborator shall agree to permit use of the Multi-Party Data from the clinical trial by any other Collaborator solely to the extent necessary to allow said other Collaborator to develop, obtain regulatory approval or commercialize its own Agent.
 - c) Any Collaborator having the right to use the Multi-Party Data from these trials must agree in writing prior to the commencement of the trials that it will use the Multi-Party Data solely for development, regulatory approval, and commercialization of its own Agent.
3. Clinical Trial Data and Results and Raw Data developed under a Collaborative Agreement will be made available to Collaborator(s), the NCI, and the FDA, as appropriate and unless additional disclosure is required by law or court order as described in the IP Option to Collaborator (http://ctep.cancer.gov/industryCollaborations2/intellectual_property.htm). Additionally, all Clinical Data and Results and Raw Data will be collected, used and disclosed consistent with all applicable federal statutes and regulations for the protection of human subjects, including, if applicable, the *Standards for Privacy of Individually Identifiable Health Information* set forth in 45 C.F.R. Part 164.
4. When a Collaborator wishes to initiate a data request, the request should first be sent to the NCI, who will then notify the appropriate investigators (Group Chair for Cooperative Group studies, or PI for other studies) of Collaborator's wish to contact them.

5. Any data provided to Collaborator(s) for Phase 3 studies must be in accordance with the guidelines and policies of the responsible Data Monitoring Committee (DMC), if there is a DMC for this clinical trial.

6. Any manuscripts reporting the results of this clinical trial must be provided to CTEP by the Group office for Cooperative Group studies or by the principal investigator for non-Cooperative Group studies for immediate delivery to Collaborator(s) for advisory review and comment prior to submission for publication. Collaborator(s) will have 30 days from the date of receipt for review. Collaborator shall have the right to request that publication be delayed for up to an additional 30 days in order to ensure that Collaborator's confidential and proprietary data, in addition to Collaborator(s)'s intellectual property rights, are protected. Copies of abstracts must be provided to CTEP for forwarding to Collaborator(s) for courtesy review as soon as possible and preferably at least three (3) days prior to submission, but in any case, prior to presentation at the meeting or publication in the proceedings. Press releases and other media presentations must also be forwarded to CTEP prior to release. Copies of any manuscript, abstract and/or press release/ media presentation should be sent to:

Email: [contact]

The Regulatory Affairs Branch will then distribute them to Collaborator(s). No publication, manuscript or other form of public disclosure shall contain any of Collaborator's confidential/proprietary information.

13.5.1 Material Transfer Agreement (MTA)

A Material Transfer Agreement (MTA) is in process in order to receive specimens from participating sites for storage and future analysis.

14 STATISTICAL CONSIDERATIONS

14.1 PRIMARY ENDPOINT, STRATIFICATION, AND SAMPLE SIZE JUSTIFICATION

The study is to test the hypothesis that patients in the TICE BCG+PANVAC arm have better recurrence-free survival than patients in the TICE BCG alone arm. Patients to be accrued to the study are adults with high grade non-muscle invasive bladder cancer who failed at least 1 induction course of BCG. These patients comprise 3 subgroups, namely, BCG persistent with one failure of BCG induction course, BCG persistent with 2 or more failures of BCG induction courses, and BCG relapsing that can behave like BCG naïve. The ratio of the composition of the three subgroups is expected to be 1:5:1 with the majority of the patients being BCG persistent and having failed 2 or more BCG induction courses. In order to achieve the balance of treatment in each subgroup, stratified randomization will be implemented in this study. However, although the three subpopulations have different recurrence-free survival experience and may respond to treatment benefit differently, the study is powered to test the overall treatment benefit of BCG+PANVAC on the entire patient population.

In the first subgroup of BCG persistent patients with one failure of BCG induction course, it is assumed that the 1-year recurrence-free survival rate is 37.5% ^{7,8} in the TICE BCG alone arm and 65% in the TICE BCG+PANVAC arm.^{38,39} Under the assumption of exponential distribution for the recurrence-free survival in both arms, the difference in recurrence-free at 1-year corresponds to hazard ratio (HR) of 2.277. In the second subgroup of BCG persistent patients with 2 or more failures of BCG induction courses, the 1-year recurrence-free survival rate in the TICE BCG alone arm is expected to be 20%.⁴⁰ Assume that the treatment benefit of TICE BCG+PANVAC in the second subgroup is lower than in the first subgroup and HR is set at 2, which corresponds to a one-year recurrence-free survival of 44.7% in the TICE BCG+PANVAC arm. In the third subgroup of BCG relapsing patients, it is expected that the 1-year recurrence-free survival rate is 48% and 65% in the TICE BCG alone and TICE BCG+PANVAC arm, respectively. This corresponds to HR=1.70.

Patient accrual is targeted at one patient per month during the first 6 months and 2 patients per month afterwards, and follow-up period after completing accrual will be 12 months. The power calculation was based on one-sided log-rank test at 15% significance level. Sample size, power and duration of the study are presented in the table below. With a total number of 49 patients, the power is 84% (see table below). Under this scenario, the expected number of events (recurrence or death) is 40. In order to allow for the possibility of a small number of unevaluable patients, the accrual ceiling will be set at 54 patients.

	Subgroup 1 1-year recurrence-free survival for BCG persistent patients who failed 1 BCG induction course	Subgroup 2 1-year recurrence-free survival for BCG persistent patients who failed 2 or more BCG induction courses	Subgroup 3 1-year recurrence-free survival for BCG naïve patients	Total sample size	Power (%)	Duration of accrual (months)	Expected number of events (recurrence or death)
Treatment benefit	HR=2.277 1-year RFS: BCG alone: 37.5% BCG+PANVAC: 65%	HR=2 1-year RFS: BCG alone: 20% BCG+PANVAC: 44.7%	HR=1.7 1-year RFS: BCG alone: 48% BCG+PANVAC: 65%	49	84	28	40

One interim analysis for futility will be performed according to the stopping procedure.³⁹ Specifically, the interim analysis will be performed when half of the expected events (20) have been observed. At that time, if the observed event rate of the TICE BCG+PANVAC arm is higher than that of the TICE BCG alone arm (i.e. the hazard ratio ≥ 1), we would consider terminating the trial and concluding that an advantage for the BCG+PANVAC regimen has not been established.

For the purpose of protecting patient safety, we implement the following stopping rule for safety monitoring of patients who receive the combination therapy.

If one patient experiences a grade 5 event, thought to be possibly or probably due to the combination therapy, the study will be stopped. For grade 3 or 4 event, the study will be stopped according to the following stopping rule. These adverse events are described in more detail in Section 7.

Number of patients	No. of grade 3 or 4 serious adverse events
3-9	3
10-18	4
19-26	5

The operating characteristic of the stopping rule was assessed by simulations. Based on 10,000 simulations, the probability of stopping early for an excess of serious adverse event over the course of trial is 0.04 when the serious adverse event rate is at the anticipated level of 6% and 0.94 when the serious adverse event rate is 30%. This is deemed reasonable for protecting patient safety.

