4.3 RANDOMIZATION PROCEDURES

There are two arms to this study and subjects will be randomized equally to either the TICE BCG arm or the combination arm of TICE BCG + PANVAC™. The study arms are described in detail below in Section [5.1](#). The arms will be stratified during randomization for TICE BCG

subgroup based on number of previous induction courses and time of recurrence. This is described in more detail along with the statistical analysis in the statistical section (Section 14).

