14.2 SECONDARY ENDPOINTS

Using Kaplan-Meier methods, we will estimate the probability distribution of progression-free survival and the time to recurrence. Results will be summarized by point estimates (12 months) with 95% CI. Exploratory analyses of these secondary objectives will compare the two treatment arms using the log rank test. Fisher's exact test will be used to compare frequency distributions of toxicity grades between the two arms.

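### Randomisation is stratified by three BCG subgroups, but Section 14 carries no strata into any test or hazard ratio; fix the stratified form in advance (a free improvement, not a power error)

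*Combined protocol and SAP*

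**What the plan says.** Section 14.1 defines three subgroups: BCG-persistent after one failed induction course, BCG-persistent after two or more, and BCG-relapsing. It states that their recurrence-free survival differs and adds: "In order to achieve the balance of treatment in each subgroup, stratified randomization will be implemented in this study". On the mix it says "The ratio of the composition of the three subgroups is expected to be 1:5:1". Section 4.3 specifies equal allocation and sends the reader to Section 14 for the detail of the stratification and the accompanying analysis.

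The log-rank appears twice in Section 14. In 14.1 it describes the sample-size work: "The power calculation was based on one-sided log-rank test at 15% significance level". In 14.2 exploratory analyses of the secondary endpoints "will compare the two treatment arms using the log rank test". Neither sentence mentions strata. No sentence states the form of the primary test. The futility rule in 14.1 acts at 20 events if the observed hazard ratio is 1 or more, without naming the estimator.

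**The concern.** Once randomisation is balanced within prognostic groups, the treatment difference varies less from trial to trial than an unstratified log-rank assumes. That test then rejects too rarely under the null, and pooling groups with different hazards pulls the estimated hazard ratio towards 1. A stratified test and a stratified Cox model use the balance that the design has already created.

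The second issue is freedom of choice. With about 40 events, an open-label design and a one-sided 15% level, two defensible versions of the same test can fall on opposite sides of the critical value. The same holds at the futility look, where the decision turns on which side of 1 the estimate falls.

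**Working it through.** **Inputs (Section 14.1 unless noted).** 49 patients in ratio 1:5:1, so 7, 35 and 7; equal allocation (4.3); exponential survival; one patient a month for 6 months, then two a month; 12 months of follow-up after accrual. The table gives 28 months of accrual, so the data cut is at month 28 + 12 = 40. The one-sided critical value is z(0.85) = 1.036. Monthly hazard = −ln(1-year survival)/12:

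| Subgroup | n | BCG alone | BCG + PANVAC | Hazard ratio | Expected events by month 40 |
|---|---|---|---|---|---|
| Persistent, 1 failure | 7 | 37.5%, 0.0817 | 65%, 0.0359 | 2.277 | 5.0 |
| Persistent, 2+ failures | 35 | 20%, 0.1341 | 44.7%, 0.0671 | 2.00 | 30.3 |
| Relapsing | 7 | 48%, 0.0612 | 65%, 0.0359 | 1.70 | 4.7 |

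Expected events per subgroup and arm are (n/2) × the average over entry times e of [1 − exp(−hazard × (40 − e))].

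**The plan's own figures.** The last column sums to 40.0, against the plan's statement: "Under this scenario, the expected number of events (recurrence or death) is 40". Simulated power of the unstratified test is 84.0% under simple randomisation and 85.0% with exact balance within strata, against the stated 84%. As a cross-check, the pooled 1-year rates are (37.5 + 5×20 + 48)/7 = 26.5% and (65 + 5×44.7 + 65)/7 = 50.5%. These imply a hazard ratio of ln(0.265)/ln(0.505) = 1.944. Schoenfeld's formula then gives Φ(√(40/4) × ln 1.944 − 1.036) = Φ(2.102 − 1.036) = 85.7%. The stated design reproduces.

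**Level at nominal 15%, balance within strata 7/35/7.** One simulation of 200,000 trials gives 14.4% unstratified and 15.5% stratified. A separate one of 40,000 trials per scenario gives 14.5 to 14.6% and 15.2 to 15.3%. With permuted blocks of 4 (an assumed block size) the levels are 14.4% and 15.6%.

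**Power at the nominal critical value.** Month-40 cut: 85.0% unstratified and 85.5 to 85.7% stratified. Follow-up capped at 12 months per patient: 79.4% and 80.1%.

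**Power with both tests calibrated to exactly 15%.** Month 40: 85.4% unstratified and 85.2% stratified in one simulation, 85.8% and 85.4% in another. Twelve months: 80.2% and 79.8%. The gain at the nominal critical value therefore comes from the stratified test's slightly higher actual level.

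**Estimate.** The mean one-step log hazard ratio (combination over BCG alone) is −0.69 unstratified against −0.73 stratified at month 40, and −0.69 against −0.71 at 12 months. The ratios are 0.69/0.73 = 0.945 and 0.69/0.71 = 0.972. These are rounded inputs; the attenuation is about 3 to 5%.

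**Agreement.** On the same simulated data the two tests reach opposite conclusions in about 4 to 6% of trials (highest in any run: 6.7%, null, month 40). If whichever test was significant were reported, the type I error would be (level 1 + level 2 + disagreement)/2. At month 40 this is (14.4 + 15.5 + 6.7)/2 = 18.3%. Direct counting gave 18.5% at month 40 and 17.0% at 12 months.

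**The case against.** The strongest reply is that there is no error to correct. A test that runs at 14.5% when 15% is allowed is valid, and it is the stratified version that slightly exceeds its level, because two strata hold about 7 patients each. Some 71% of patients (5/7) are in one stratum, so stratifying changes little. Section 14.1 aims at the overall benefit in the whole population, for which an unstratified comparison is legitimate. The comparisons in 14.2 are labelled exploratory. All of this stands.

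Two stronger readings are tempting, and the documents support neither. A reader might infer that the primary test is an unstratified log-rank. The sentence in 14.1 describes the power calculation, and the form of the primary test is simply not stated. A reader might also infer that the plan wastes power or that 84% is wrong. The unstratified test reaches 84 to 85% under the plan's assumptions, and at equal actual level stratification adds nothing.

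The reply does not remove the gap. Section 4.3 points to Section 14 for the analysis that goes with the stratification, and none is there. The average difference between the tests is small, but individual trials can turn on the choice. Nothing suggests that the investigators would pick the favourable result, so the 17 to 18.5% figure is an upper limit on what the open choice could cost, not a prediction.

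**Conclusion.** This is a specification gap worth closing, as a free improvement. Neither the sample size nor the stated power needs to change. Left unstratified, the log-rank would run about half a point below its nominal 15% and the log hazard ratio would be about 3 to 5% smaller than the stratified one. Stratified, the test runs about 0.2 to 0.5 point above nominal, which is immaterial at a 15% level. The practical reason to act is the 4 to 6% of trials in which the conclusion depends on the version used.

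The figures assume the plan's survival rates, its 1:5:1 mix, exponential times and near-exact balance within strata. Equal-sized strata (16/16/17) gave a similar picture: unstratified level 14.2%, and power 82.1% unstratified against 82.6% stratified. The futility look was not simulated. Halving the expected events suggests only 2 to 3 in each small stratum at 20 events, so the case for stratifying there is consistency with the final analysis, not a demonstrated gain.

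**What to change.** In 14.1, state that the primary test is a one-sided log-rank at 15%, stratified by the three subgroups as recorded at randomisation. State that the hazard ratio comes from a Cox model stratified in the same way, and that this estimate is used at the 20-event futility look. Say the same for the log-rank comparisons in 14.2. Name the unstratified log-rank and hazard ratio as a sensitivity analysis.

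The cost is one or two sentences. The subgroup is already needed for randomisation, so no new data, patients or visits are required, and 49 patients and 84% power can stay as stated.

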- We hypothesize that the combined administration of BCG and PANVAC™ may augment the BCG-induced cytotoxic T lymphocyte response against bladder cancer cells expressing MUC-1 and/or CEA and potentially reverse BCG failure in patients that have failed one induction course of BCG

Objectives:

- To determine if there is an improvement in disease-free survival (DFS*) with BCG + PANVAC compared with BCG alone in a phase II study in non-muscle invasive high-grade urothelial carcinoma of the bladder who have failed to respond to intravesical BCG.

*within 1 year post treatment

Eligibility:

- Individuals who have failed at least one previous induction course of intravesical BCG, defined as histologically confirmed persistent or relapsing tumor present on post-BCG endoscopic evaluation. All BCG failures will be considered for inclusion into the study, including BCG-refractory, -resistant, and -relapsing, as defined in the “Rationale and Background.” For the purposes of the study, “BCG-refractory” and “BCG-resistant” subjects will be considered to have “BCG-persistent” disease.
- Patients who are not currently candidates for radical cystectomy (e.g. patient refuses surgery, comorbidities preclude major surgery, etc.).
- Normal organ function, ECOG 0-2.

Design:

- This is a randomized, open label prospective, Phase II study in subjects with non-muscle invasive high grade urothelial carcinoma of the bladder who have failed at least one induction course of intravesical BCG, randomized to one of the following arms: TICE BCG +PANVACTTM or TICE BCG alone. Randomization is stratified by BCG treatment subgroup.
- All subjects will receive intravesical TICE BCG (50mg) as per usual standard of care once weekly (+/- 2 days) starting in week 3 for a total of 6 weeks.
- The combination arm will receive the pox viral vaccines that contain the transgenes for CEA and MUC-1 (both with modified HLA-A2 agonist epitopes) as well as 3 human T-cell costimulatory molecules, B7-1, ICAM-1, and LFA-3 [rV-PANVACTTM (vaccinia) and rF-PANVACTTM (fowlpox)] as follows:
 - rV-PANVACTTM 2 x 10⁸ pfu SQ at week 0 (+/- 7 days) only.
 - rF-PANVACTTM 1 x 10⁹ pfu SQ at weeks (+/- 7 days) 3, 7, 11, and 15.
- For this Phase II study, we will test the hypothesis that subjects in the TICE BCG +PANVACTTM arm have better disease-free survival than subjects in the TICE BCG alone arm.

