1.3.9 To assess production of urinary cytokines and chemokines in collected samples

2 BACKGROUND

Bladder cancer accounts for the 4th most common cancer in men and the 12th most common cancer in women. An estimated 73,510 people living in the United States will be diagnosed with

bladder cancer in 2012, with approximately 14,880 dying of bladder cancer in the same year.¹ Most of these patients (>75%) will be diagnosed with non-muscle invasive bladder cancer and approximately 50% of these patients will present with high grade disease.² High grade non-muscle invasive bladder cancer (Ta, T1, and/or CIS) is difficult to treat because of high rates of recurrence and progression. The last major advance in bladder cancer therapy was the approval of bacillus Calmette-Guerin (BCG) in 1990 by the FDA.³ Currently, intravesical BCG given as an induction course (6 weeks of intravesical therapy) is the standard of care^{4,5} followed by maintenance therapy. BCG has an initial failure rate of ~35% in terms of disease recurrence or progression. In ~20-35% of cases that failed an initial induction course of BCG, a second course of induction BCG may be beneficial, but patients who fail two courses are often best served by radical cystectomy.⁶⁻⁸ Patients with CIS alone may respond at a higher rate to a second induction course, however, cystectomy may still be required in at least 1/3 of these patients. This surgery involves the en bloc removal of the bladder and adjacent organs (prostate in males and uterus in females) and concomitant creation of a urinary diversion, which can affect a patient's quality-of-life significantly. Moreover, Shabsigh et al. reported that 64% of patients who undergo cystectomy suffer at least one complication within the first 90 days after surgery⁹ and the operation has been reported to have at least a 2.5% perioperative mortality rate even at a high-volume center.¹⁰ This fact is reflected in a 2003 survey, which showed that 81% of urologists were reluctant to refer their patients to radical cystectomy despite failing 2 courses of intravesical therapy.¹¹ In summary, radical cystectomy has the potential for significant morbidity and therefore, an unmet clinical need for intravesical therapy exists for these high grade non-muscle invasive bladder cancers that fail BCG.

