3 PATIENT SELECTION

3.1 ELIGIBILITY CRITERIA

3.1.1 Inclusion Criteria

- 3.1.1.1 Patients must have histologically confirmed localized high grade (G3) transitional cell carcinoma (urothelial carcinoma) of the bladder that is stage Ta, T1, and/or CIS

confirmed by the Laboratory of Pathology, NCI 90 days prior to study entry. This can be obtained at an outside hospital prior to entry into the study or at the NCI. However, all outside pathology specimens will require that the formalin-fixed paraffin embedded tissues be re-read by the Laboratory of Pathology, NCI. For patients enrolled at collaborating trial sites, diagnosis must be confirmed by the Department of Pathology at the institution where the patient is enrolled on the trial. Pathology can also be reviewed by the Laboratory of Pathology at the NCI if the participating trial site prefers another pathologic evaluation.

- 3.1.1.2 Patients have failed at least one previous induction course of intravesical BCG, defined as histologically confirmed persistent or relapsing tumor present on post-BCG endoscopic evaluation. All BCG failures will be considered for inclusion into the study, including BCG-refractory, -resistant, and -relapsing, as defined in the “Rationale and Background.” For the purposes of the study, “BCG-refractory” and “BCG-resistant” subjects will be considered to have “BCG-persistent” disease.
- 3.1.1.3 Patients who are not currently candidates for radical cystectomy (e.g. patient refuses surgery, comorbidities preclude major surgery, etc.).
- 3.1.1.4 Age ≥ 18 years.

Because no dosing or adverse event data are currently available on the use of BCG in combination with PANVAC™ in patients <18 years of age, children are excluded from this study.

- 3.1.1.5 ECOG performance status ≤ 2 (see Appendix A, Section 17.1).

- 3.1.1.6 Patients must have normal organ and marrow function as defined below:

- absolute neutrophil count	$\geq 1,500/\text{mcL}$
- platelets	$\geq 50,000/\text{mcL}$
- total bilirubin	$\leq 1.5 \times$ institutional upper limit of normal
- AST(SGOT)/ALT(SGPT)	$\leq 3 \times$ institutional upper limit of normal
- estimated GFR (calculated using CKD-EPI equation)	$\geq 30 \text{ mL/min}/1.73 \text{ sq.m.}$

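### A chance imbalance in CIS-alone disease between arms would go uncorrected in the primary recurrence-free survival test, although CIS status is available at entry

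*Combined protocol and SAP*

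**What the plan says.** Section 2 (Background) singles out one tumour type as possibly prognostic: "Patients with CIS alone may respond at a higher rate to a second induction course". It adds that a third or more of them may still come to surgery, and gives no response rate or recurrence-free survival by CIS status.

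Section 3.1.1 requires, for every patient, "histologically confirmed localized high grade (G3) transitional cell carcinoma (urothelial carcinoma) of the bladder that is stage Ta, T1, and/or CIS". CIS status can therefore be read from the entry pathology before treatment starts.

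The précis states: "Randomization is stratified by BCG treatment subgroup". Section 4.3 defines that as a "subgroup based on number of previous induction courses and time of recurrence", and Section 14.1 lists the three groups: "namely, BCG persistent with one failure of BCG induction course, BCG persistent with 2 or more failures of BCG induction courses, and BCG relapsing". CIS status cuts across these groups.

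For the primary endpoint, Section 14.1 says only: "The power calculation was based on one-sided log-rank test at 15% significance level". It does not say that the BCG strata enter the test, and it names no covariate. No CIS-adjusted or CIS sensitivity analysis appears in Section 14.

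**The concern.** A baseline factor that the protocol itself flags, and that eligibility already requires, plays no part in the comparison that decides the trial. Randomisation balances it only in expectation. With about 24 or 25 patients per arm, a sizeable chance difference in CIS-alone share is not rare. If the factor is prognostic, the unadjusted log-rank test carries that difference straight into the result. The one-sided threshold of 0.15 is lenient, so a modest shift can move the p-value across it. Leaving out a prognostic factor may also cost some power.

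**Working it through.** **Inputs from Section 14.1.** 49 patients; subgroup mix 1:5:1 (7, 35, 7); 1-year rates 37.5% v 65%, 20% v 44.7% and 48% v 65%; accrual 1 per month for 6 months, then 2 per month; 12 months of further follow-up; one-sided level 0.15.

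**Reproducing the plan.** Hazard ratios: ln 0.375 / ln 0.65 = 2.277; ln 0.20 / ln 0.447 = 2.0; ln 0.48 / ln 0.65 = 1.70. Exponential survival with a data cut at month 40 gives 40.0 expected events (stated: 40). Simulating the unstratified log-rank test gives about 85% power (stated: 84%). As a cross-check, the mean log hazard ratio is (0.823 + 5 × 0.693 + 0.533)/7 = 0.689. The Schoenfeld formula then gives Φ(0.689 × √40/2 − 1.036) = Φ(1.14) = 0.87, slightly high because it ignores subgroup heterogeneity. The plan's figures hold.

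**Assumptions not in the documents.** CIS-alone share 15-50%; recurrence hazard ratio for papillary v CIS alone from 1 to 4; no dropout; no futility look. Each stratum's 1-year control rate is kept at its stated value.

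**Chance of imbalance.** For share p, the standard deviation of the arm difference is √[p(1−p)(1/24 + 1/25)]. At p = 0.30 this is √(0.21 × 0.0817) = 0.131, so P(difference ≥ 0.15 in either direction) = 2[1 − Φ(1.145)] ≈ 25%. At p = 0.15 it is about 14%. Simulation under stratified randomisation gives 15-28% across the assumed shares. At a 30% share, about 13% of randomisations have such an imbalance favouring the combination arm.

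**Effect of an imbalance.** At a hazard ratio of 2, a 15-point difference shifts the log hazard ratio by about 0.15 × ln 2 = 0.10. The standard error with 40 events is 2/√40 = 0.32, so the shift is about 0.33 standard errors. The conditional false-positive rate is then about 1 − Φ(1.036 − 0.33) = 24%. Imbalances of 15 points or more average somewhat larger. Simulated results, given such an imbalance and the test without CIS:

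| Hazard ratio, papillary v CIS alone | False-positive rate, imbalance favours combination | Power, imbalance against it |
|---|---|---|
| 1.4 | about 20% | 75-80% |
| 2 | 25-28% | 68-70% |
| 3 | 35-36% | 50-60% |

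Adjusting for CIS at a hazard ratio of 2 returns the false-positive rate to about 14-16%. Averaged over all randomisations, the unadjusted test rejects a true null in 14-15% of trials.

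**Average power at a 30% CIS-alone share.** Set-up A compares the plain log-rank with a Cox model adding CIS, with the data cut at month 40. Set-up B compares the BCG-stratified test without and with a CIS covariate, assessed at scheduled looks.

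| Hazard ratio | A: without → with CIS | B: without → with CIS |
|---|---|---|
| 1 | 85.7 → 85.2% | 83.3 → 83.6% |
| 1.4 (A) / 1.5 (B) | 84.4 → 84.5% | 82.4 → 83.2% |
| 2 | 81.8 → 84.0% | 80.3 → 82.0% |
| 2.6 (B) | – | 78.4 → 81.3% |
| 3 (A) | 77.5 → 83.8% | – |
| 4 (B) | – | 72.2 → 79.6% |

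In set-up A the gain across shares of 15-50% is 1.5-3 points at a hazard ratio of 2 and 3-7 points at 3. A further run with B's strata gave about 1, 2, 4 and 9 points at 1.5, 2.0, 2.6 and 4.0, and a loss of at most about 1 point with no CIS effect.

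**Effect confined to the other two subgroups.** If CIS matters only in the 14 patients outside the group with two or more failed courses, power without/with the covariate is 83.5/82.8%, 83.4/82.8%, 83.7/83.7% and 83.8/83.8% at hazard ratios 1.5, 2.0, 2.6 and 4.0. There is no gain.

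**Type I error in B.** Stratified test 0.146-0.156; with the CIS covariate 0.151-0.165.

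**The case against.** The strongest case is that the Background sentence supports little. It says patients with CIS alone may respond better, and it concerns a second course. Section 14.1 expects 5/7 of patients (35 of 49, 71%) to have failed two or more courses, so they receive at least a third. If the effect does not extend to them, the power argument disappears. This stands.

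A reader might infer from the Background that CIS alone carries a hazard ratio of 2.6-4.0: ln 0.35 / ln 0.667 = 2.6 and ln 0.20 / ln 0.667 = 4.0. The documents do not support that. The 2/3 comes from a statement about needing cystectomy, which is not recurrence; it is a ceiling, because the text says at least 1/3; and it has no time horizon. The 20-35% comparator covers all patients failing a first course, not papillary disease. The range serves only as a strong-effect scenario.

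The gain at moderate effects is also small, and in the BCG-stratified form it is partly bought with type I error: testing at 0.16 instead of 0.15 is itself worth about 1.2 points of power near 80%. With size corrected, one run gave a gain of 0 at a hazard ratio of 1.5 and 0.7 points at 2. This too stands.

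Finally, a shift of 0.10 is only a third of a standard error, the planned test is valid overall, and the Background gives a reason for stratifying by BCG-failure type. All true. None of it answers the conditional problem: once the arms happen to differ, the plan has no correction, and the data for one are already required.

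**Conclusion.** The point holds as a modest, conditional weakness. CIS status is available for everyone, is flagged as possibly prognostic, and is absent from the only primary test named. The case for adjustment is protection against a realised imbalance: about a 15-28% chance of 15 points or more in either direction and, if the hazard ratio were 2 in all strata, a false-positive rate of about 25-28% when the imbalance favours the combination arm.

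Two stronger conclusions might be drawn, and neither is supported. One is that the plan gives away a definite amount of power. The loss depends on a share and an effect that the documents do not state: about 0 if the effect is weak or confined to the two smaller subgroups, about 1.5-3 points at a hazard ratio of 2 in all strata, and about 3-9 points only at 2.6-4.0. The other is that the randomisation is deficient. Adding CIS to it while keeping the unadjusted test gains at most about 1 point.

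**What to change.** In Section 14.1, before outcomes by arm are examined, pre-specify the primary comparison as a covariate-adjusted log-rank (Cox score) test, stratified by BCG subgroup, with one baseline covariate: CIS alone versus papillary disease (Ta/T1 with or without CIS), taken from the entry pathology. The definition is needed because "of the bladder that is stage Ta, T1, and/or CIS" also admits papillary disease with concomitant CIS. Keep the log-rank without CIS as a sensitivity analysis.

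Do not cross CIS with the BCG strata. Two of those strata hold about seven patients each, and splitting them again can lose power (about 1 point at a weak effect). Leave the randomisation unchanged.

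The cost is one sentence and one coded variable from pathology already required. The downsides are a type I error of about 0.15-0.165 with the asymptotic variance, which a re-randomisation p-value removes, and up to about 1 point of power if CIS has no effect.

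If outcomes by arm have already been examined, report the adjusted test as a labelled sensitivity analysis. This needs checking first: Section 14.1 plans a futility look that compares the arms at 20 events, and Section 8 records that the study closed with CTEP on 5/1/2019.
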